### **7.6. Toxicity Management**

All clinical and clinically significant laboratory toxicities will be managed according to uniform guidelines below.

#### **ALT Elevation or Flare Management**

Subjects with on-treatment serum ALT elevation  $> 2 \times$  nadir or  $> 2 \times$  Baseline value and  $\geq 5 \times$  ULN, with or without associated symptoms should be managed according to the guidance below.

All on-treatment elevated serum ALT should be confirmed as soon as possible and ideally within 3 days of receipt of results. During the visit, a clinical assessment of the subject should be performed. The assessment should include a physical examination, evaluation of the subject's mental status and the following laboratory tests:

- Laboratory parameters: serum ALT and AST, total bilirubin, INR and serum albumin.
- If the ALT elevation is confirmed, the central clinical laboratory will conduct reflex testing for plasma HBV DNA, serology for HBV (HBsAg, HBsAb, HBeAg and HBeAb), HDV, HAV IgM, HCV, and HEV.

**For GS-9992 Management**

Based on the results of the confirmatory tests, the following treatment modifications for GS-9992 are recommended:

**Table 7-1. GS-9992 Dose Modification and Monitoring**

Liver Toxicity	Action
Confirmed ALT $\geq 10 \times$ ULN without evidence of hepatic toxicity as defined below	Discuss with the Medical Monitor if GS-9992 should be dose reduced by 50% or discontinued if the safety of the subject is of immediate concern. Subject should be monitored weekly or more frequently if clinically indicated until ALT $< 5 \times$ ULN
Confirmed ALT $> 2 \times$ nadir, with evidence of hepatic toxicity, defined as any one of the following: 
 
• Total bilirubin <math>> 2 \times</math> baseline or nadir AND <math>> \text{ULN}</math> in the absence of Gilbert's disease
 
• Elevated INR <math>> 0.5</math> above baseline AND <math>> \text{ULN}</math>
 
• Abnormal serum albumin <math>> 1 \text{ g/dL}</math> decrease from baseline
 
	Permanently discontinue GS-9992. Subject should be monitored weekly until ALT $< 5 \times$ ULN, and total bilirubin and INR values return to normal or baseline levels
Confirmed ALT $> 2 \times$ Baseline and $\geq 5 \times$ ULN without evidence of hepatic toxicity, as defined above	Continue GS-9992, ALT should be evaluated every 2 weeks or more frequently as clinically needed, until ALT $< 5 \times$ ULN

**For TAF Management**

Based on the results of the confirmatory tests, the following treatment modifications for TAF are recommended:

**Table 7-2. TAF Dose Modification and Monitoring**

Liver Toxicity	Action
Confirmed ALT levels $\geq 10 \times$ ULN, with evidence of hepatic toxicity, defined as any one of the following: 
 
• Total bilirubin <math>> 2 \times</math> baseline or nadir AND <math>> \text{ULN}</math> in the absence of Gilbert's disease
 
• Elevated INR <math>> 0.5</math> above baseline AND <math>> \text{ULN}</math>
 
• Abnormal serum albumin <math>> 1 \text{ g/dL}</math> decrease from baseline
 
	Discuss with the Medical Monitor if TAF should be discontinued, unless the safety of the subject is of immediate concern. Subject should be monitored weekly as long as ALT, total bilirubin and INR values remain elevated or above baseline values. If the ALT values remain persistently elevated, the investigator should discuss with the Medical Monitor if TAF should be discontinued.
Confirmed ALT levels $\geq 10 \times$ ULN, without evidence of hepatic toxicity, as defined above	Continue TAF and monitor weekly until ALT values return to normal or baseline levels. If the ALT values remain persistently elevated, the investigator should discuss with the Medical Monitor if TAF should be discontinued.

Specific toxicity discontinuation criteria in Section 6.11 supersede below general toxicity guidelines, and in general, where discrepancy is present, the more conservative criteria apply. The Gilead Medical Monitor should be consulted prior to study drug discontinuation when medically feasible.

#### **7.6.1. Grades 1 and 2 Laboratory Abnormality or Clinical Event**

- Continue investigational medicinal product at the discretion of the investigator.

#### **7.6.2. Grade 3 Laboratory Abnormality or Clinical Event**

- For Grade 3 clinically significant laboratory abnormality or clinical event, investigational medicinal product may be continued if the event is considered to be unrelated to investigational medicinal product.
- For a Grade 3 clinical event, or clinically significant laboratory abnormality (except ALT evaluations) confirmed by repeat testing, that is considered to be related to investigational medicinal product, investigational medicinal product should be withheld until the toxicity returns to  $\leq$  Grade 2.

#### **7.6.3. Grade 4 Laboratory Abnormality or Clinical Event**

- For a Grade 4 clinical event or clinically significant Grade 4 laboratory abnormality confirmed by repeat testing that is considered related to investigational medicinal product, investigational medicinal product should be permanently discontinued and the subject managed according to local practice. The subject should be followed as clinically indicated until the laboratory abnormality returns to baseline or is otherwise explained, whichever occurs first. A clinically significant Grade 4 laboratory abnormality that is not confirmed by repeat testing should be managed according to the algorithm for the new toxicity grade.
- Investigational medicinal product may be continued without dose interruption for a clinically non-significant Grade 4 laboratory abnormality (e.g., Grade 4 CK after strenuous exercise, or triglyceride elevation that is non-fasting or that can be medically managed) or a clinical event considered unrelated to investigational medicinal product.

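### For a confirmed, clinically significant, drug-related ALT above 10 x ULN without hepatic toxicity, protocol Section 7.6.3 contradicts Tables 7-1 and 7-2, and the precedence sentence does not give one clear answer

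*Protocol*

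**What the plan says.** Appendix 3 of the protocol grades ALT above 5 to 10 x ULN as Grade 3 and above 10 x ULN as Grade 4.

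Section 7.6.3 applies to a "clinically significant Grade 4 laboratory abnormality confirmed by repeat testing that is considered related to investigational medicinal product". The action is that "investigational medicinal product should be permanently discontinued and the subject managed according to local practice". Its second bullet says that the product "may be continued without dose interruption for a clinically non-significant Grade 4 laboratory abnormality", with creatine kinase after exercise and triglycerides as examples. ALT is not mentioned.

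Two neighbouring rules do except ALT. Section 7.6.2 (Grade 3) covers a "clinically significant laboratory abnormality (except ALT evaluations) confirmed by repeat testing". Section 6.11 excludes isolated ALT elevations from its discontinuation criterion for related abnormalities of Grade 3 or higher.

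ALT has its own guidance in Section 7.6. For confirmed ALT of at least 10 x ULN without hepatic toxicity, Table 7-1 says "Discuss with the Medical Monitor if GS-9992 should be dose reduced by 50% or discontinued", followed by a clause about immediate concern for the subject's safety. Table 7-2 says "Continue TAF and monitor weekly until ALT values return to normal or baseline levels".

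The sentence after Table 7-2 places the criteria of 6.11 above the general guidelines that follow it, and adds that, in general, "where discrepancy is present, the more conservative criteria apply". Section 6.11 in turn sends the reader to 7.6 for further discontinuation criteria. The synopsis repeats the two tables' actions for this case and the 6.11 criteria, but neither the 7.6.3 rule nor the precedence sentence.

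**The concern.** One laboratory result can fall under three instructions that do not agree. A site following the tables could reduce GS-9992 and keep the subject on TAF. A site following 7.6.3 would stop study product permanently. If it took that to mean both drugs, a viremic subject would move into treatment-free follow-up.

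This is first a safety matter. Section 1.4.1 names the liver as the only target organ of toxicity in the preclinical studies. The longest human experience described there is 12 weeks at up to 200 mg, while Group 5 receives 400 mg. The Group 5 dosing hold in 6.11 also leaves out isolated ALT elevations, so the individual-subject rules in 7.6 carry this risk.

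It also reaches the primary endpoint, because the choice of rule can decide whether a subject has an on-treatment Week 12 HBsAg value at all.

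**Working it through.** **Text check.** Take a confirmed ALT of 11 x ULN, judged clinically significant and drug-related, with bilirubin, INR and albumin not meeting the hepatic-toxicity definition.

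1. Appendix 3: 11 is above 10, so Grade 4. At exactly 10 x ULN the value is Grade 3, so the conflict begins strictly above 10.
2. Section 7.6.3: permanent discontinuation of study product.
3. Table 7-1: Medical Monitor discussion of a 50% GS-9992 reduction or discontinuation.
4. Table 7-2: TAF continues with weekly monitoring; stopping is discussed only if ALT stays persistently elevated.
5. Section 6.11: its laboratory criterion does not apply if the elevation is isolated, a term the protocol does not define.

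Steps 2 and 3 differ because 7.6.3 removes the reduction option. Steps 2 and 4 differ if the rise is judged TAF-related, or if the product term in 7.6.3 is read as both drugs. Section 7.2.1 has causality assessed for each product, while Section 5 treats GS-9992 and TAF alike as investigational products.

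**Precedence sentence.** Its first part ranks 6.11, not Tables 7-1 and 7-2, above 7.6.3. Section 6.11 omits isolated ALT without ordering continuation, and refers back to 7.6. Its second part, the conservative default, can be read as selecting 7.6.3, which would cancel the reduction option and the TAF continuation row for related, clinically significant cases above 10 x ULN.

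**How many subjects.** Section 1.2.2 describes one active patient above 10 x ULN across the ACHIEVE cohorts (25 to 200 mg). Documented active subjects are 16 (25 mg, taking the 16 in the efficacy paragraph as active), 16 (50 mg), 17 (100 mg) and 12 (the first 200 mg subjects reported).

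- 16 + 16 + 17 + 12 = 61; 1/61 = 1.6%.
- Groups 1, 3 and 5: 3 x 30 = 90 subjects; 90 x 1/61 = 1.5.
- Confirmed ALT flares on TAF (Section 1.3.2: above 2 x baseline and above 10 x ULN at two consecutive visits): 5 subjects, 0.6%; 90 x 0.006 = 0.5.

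Neither rate is restricted to related, clinically significant cases without hepatic toxicity, so about 0 to 2 of 90 is a fair range at these rates.

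**Primary endpoint.** SAP Section 3.8.2 counts data as on-treatment up to 3 days after the last dose of GS-9992 or TAF, whichever is later. Table 3-1 puts Week 12 HBsAg at Days 72 to 99. A subject whose last dose of both drugs is on Day 68 has on-treatment data only to Day 68 + 3 = 71, one day short of the window. Later samples go to follow-up windows, and protocol Section 8.3 counts a missing primary outcome as failure. The same subject continuing TAF can still have a Week 12 value. One subject in a group of 30 is 1/30 = 3.3 percentage points.

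**The case against.** The best defence is that ALT has its own algorithm. Section 7.6 sends ALT flares to dedicated guidance, and the 6.11 exclusion covers Grade 3 or higher and therefore Grade 4. Section 6.11 outranks the general guidelines, of which 7.6.3 is one. A natural reading is that the tables govern ALT and 7.6.3 governs everything else. That may well be the intent, but the text does not say so: it ranks 6.11 rather than the tables, and 6.11 returns the reader to 7.6.

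Several limits on the conflict stand. Section 7.6.3 requires clinical significance, and a non-significant value may continue, although nothing classes ALT above 10 x ULN without hepatic toxicity as non-significant. Table 7-1 itself lists discontinuation, and the actions in both tables are recommendations. The Medical Monitor should be consulted before discontinuation when feasible, which makes uncoordinated opposite actions less likely but does not tell anyone which rule applies.

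Three stronger readings are tempting and not supported.

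- A reader might infer that the two parts of the precedence sentence point in opposite directions. Section 6.11 only omits isolated ALT, so its part may be silent and the conservative default may decide.
- A reader might put the affected number at 2 to 6, from 90 x 18/859 = 1.9 and 90 x 1/16 = 5.6. The 1/16 uses only the ACHIEVE cohort in which the case occurred. The 18/859 counts any treatment-emergent Grade 4 ALT on TAF, confirmed or not.
- A reader might infer that the subjects affected are those most likely to respond, because a 25 mg flare patient had a 1.01 log10 HBsAg fall. That flare is documented only as above 200 IU. No HBsAg result is given for the patient above 10 x ULN.

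**Conclusion.** The contradiction is real and narrow. It needs a confirmed ALT above 10 x ULN that is clinically significant, drug-related and without hepatic toxicity. For TAF it also needs relatedness to TAF or a both-drugs reading of the product term. Within that case 7.6.3 and the tables cannot both be followed whenever the dose is reduced or TAF is continued, and the precedence sentence leaves the choice open.

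The expected number is small, about 0 to 2 of 90. This assumes that the ACHIEVE monotherapy rate and the TAF-alone rate carry over to the combination. The rate at 200 to 400 mg plus TAF is unknown and could be higher. The effect on the primary result is at most 3.3 percentage points per affected subject in a 30-subject group, and only when both drugs stop early enough to leave no on-treatment Week 12 value. The main reason to act is that a liver-safety rule should give every site the same instruction.

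**What to change.** Reconcile Sections 6.11, 7.6.2 and 7.6.3, Tables 7-1 and 7-2, and the matching synopsis text:

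- State in 7.6.3 which section governs Grade 4 ALT elevations.
- Name GS-9992 and TAF separately in 7.6.3 in place of the collective product term.
- Replace the two-part precedence sentence, as far as ALT is concerned, with one rule that gives a single answer, and define what counts as an isolated elevation.
- Carry the outcome into the synopsis.

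Which rule applies is for the sponsor's medical team to decide. The cost is protocol wording and a memo to sites, with no new procedures, visits or subjects.

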### **7.7. Special Situations Reports**

#### **7.7.1. Definitions of Special Situations**

Special situation reports include all reports of medication error, abuse, misuse, overdose, reports of adverse events associated with product complaints, occupational exposure with an AE, pregnancy reports regardless of an associated AE, and AE in an infant following exposure from breastfeeding.

Medication error is any unintentional error in the prescribing, dispensing, or administration of a medicinal product while in the control of the health care provider, subject, or consumer.

Abuse is defined as persistent or sporadic intentional excessive use of a medicinal product by a subject.

Misuse is defined as any intentional and inappropriate use of a medicinal product that is not in accordance with the protocol instructions or the local prescribing information.

An overdose is defined as an accidental or intentional administration of a quantity of a medicinal product given per administration or cumulatively which is above the maximum recommended dose as per protocol or in the product labelling (as it applies to the daily dose of the subject in question). In cases of a discrepancy in drug accountability, overdose will be established only when it is clear that the subject has taken the excess dose(s). Overdose cannot be established when the subject cannot account for the discrepancy except in cases in which the investigator has reason to suspect that the subject has taken the additional dose(s).

Product complaint is defined as complaints arising from potential deviations in the manufacture, packaging, or distribution of the medicinal product.

Occupational exposure is defined as exposure to a medicinal product as a result of one's professional or non-professional occupation.

## **7.7.2. Instructions for Reporting Special Situations**

### **7.7.2.1. Instructions for Reporting Pregnancies**

The investigator should report pregnancies in female study subjects that are identified after initiation of study medication and throughout the study, including the post study drug follow-up period, to Gilead PVE using the pregnancy report form within 24 hours of becoming aware of the pregnancy.

Refer to Section 7.3 and the eCRF completion guidelines for full instructions on the mechanism of pregnancy reporting.

The pregnancy itself is not considered an AE nor is an induced elective abortion to terminate a pregnancy without medical reasons.

Any premature termination of pregnancy (e.g., a spontaneous abortion, an induced therapeutic abortion due to complications or other medical reasons) must be reported within 24 hours as an SAE. The underlying medical reason for this procedure should be recorded as the AE term.

A spontaneous abortion is always considered to be an SAE and will be reported as described in Sections 7.1.1 and 7.1.2. Furthermore, any SAE occurring as an adverse pregnancy outcome post study must be reported to Gilead PVE.

The subject should receive appropriate monitoring and care until the conclusion of the pregnancy. The outcome should be reported to Gilead PVE using the pregnancy outcome report form. If the end of the pregnancy occurs after the study has been completed, the outcome should be reported directly to Gilead PVE. Gilead PVE contact information is as follows:

Email: **PPD** and Fax: **PPD**.

Pregnancies of female partners of male study subjects exposed to Gilead or other study drugs must also be reported and relevant information should be submitted to Gilead PVE using the pregnancy and pregnancy outcome forms within 24 hours. Monitoring of the subject should continue until the conclusion of the pregnancy. If the end of the pregnancy occurs after the study has been completed, the outcome should be reported directly to Gilead PVE, fax number PPD or email PPD.

Refer to [Appendix 4](#) for Pregnancy Precautions, Definition for Female of Childbearing Potential, and Contraceptive Requirements.

#### 7.7.2.2. Reporting Other Special Situations

All special situations reports (SSRs) will be recorded in the eCRF database within the timelines outlined in the eCRF completion guideline.

##### Electronic Special Situations Report (eSSR) Reporting Process:

Site personnel record all SSR data in the eCRF database and from there transmit the SSR information to Gilead DSPH within 24 hours of the investigator's knowledge of the event throughout the duration of the study, including the protocol-required post treatment follow-up period. Detailed instructions can be found in the eCRF completion guidelines.

If for any reason it is not possible to record the SSR information electronically, i.e., the eCRF database is not functioning, record the SSR on the paper serious adverse event reporting form and submit within 24 hours to: **Gilead PVE:** Email: PPD  
Fax: PPD

As soon as it is possible to do so, any SSR reported via paper must be transcribed into the eCRF Database according to instructions in the eCRF completion guidelines.

If an SSR has been reported via a paper form because the eCRF database has been locked, no further action is necessary. These reports must consist of situations that involve study IMP and/or Gilead concomitant medications, but do not apply to non-Gilead concomitant medications.

Special situations involving non-Gilead concomitant medications does not need to be reported on the special situations report form; however, for special situations that result in AEs due to a non-Gilead concomitant medication, the AE should be reported on the AE form.

Any inappropriate use of concomitant medications prohibited by this protocol should not be reported as "misuse," but may be more appropriately documented as a protocol deviation.

Refer to [Section 7.3](#) and the CRF/eCRF completion guidelines for full instructions on the mechanism of special situations reporting.

All clinical sequelae in relation to these special situation reports will be reported as AEs or SAEs at the same time using the AE eCRF and/or the SAE report form. Details of the symptoms and signs, clinical management, and outcome will be reported, when available.

## 8. STATISTICAL CONSIDERATIONS

### 8.1. Analysis Objectives and Endpoints

#### 8.1.1. Analysis Objectives

The primary objectives of this study are:

- To evaluate the safety and tolerability of the 12 week treatment regimens of GS-9992 plus TAF or commercially available NUC
- **Groups 1-3 and 5**

To evaluate the antiviral activity of 12 weeks of GS-9992 plus TAF versus TAF alone in viremic CHB subjects as measured by the proportion of subjects with  $\geq 0.5$  log10 IU/mL decline from Baseline at Week 12 in circulating serum HBV surface antigen (HBsAg)

- **Group 4**

To evaluate the antiviral activity of 12 weeks of GS-9992 with commercially available NUC(s) in virally suppressed CHB subjects as measured by the proportion of subjects with  $\geq 0.5$  log10 IU/mL decline from Baseline at Week 12 in circulating serum HBV surface antigen (HBsAg)

The secondary objectives of this study are:

#### **Groups 1-3 and 5**

- To evaluate the safety and tolerability of the 48 week treatment regimens as assessed by review of the accumulated safety data
- To evaluate the antiviral activity of 12 weeks of GS-9992 plus TAF versus TAF alone in CHB subjects as measured by the proportion of subjects with  $\geq 1$  log10 IU/mL decline from Baseline at Week 12 in circulating HBsAg
- To evaluate the proportion of HBeAg-positive CHB subjects who achieve HBeAg loss and seroconversion during 12 weeks of GS-9992 plus TAF versus TAF alone and after GS-9992 discontinuation through 48 weeks
- To evaluate the proportion of CHB subjects who achieve HBsAg loss during 12 weeks of GS-9992 plus TAF versus TAF alone and after GS-9992 discontinuation through 48 weeks
- To evaluate the incidence of drug resistance mutations during 48 weeks of treatment
- To characterize steady-state pharmacokinetics of study drugs

- To evaluate the change from Baseline in HBV DNA and quantitative HBsAg in CHB subjects during 12 weeks of GS-9992 plus TAF versus TAF alone and after GS-9992 discontinuation through 48 weeks

#### Group 4

- To evaluate the proportion of subjects experiencing HBV virologic breakthrough (2 consecutive visits of HBV DNA  $\geq 69$  IU/mL) during 12 weeks of GS-9992 treatment
- To evaluate the antiviral activity of 12 weeks of GS-9992 in CHB subjects as measured by the proportion of subjects with  $\geq 1$  log10 IU/mL decline from Baseline at Week 12 in circulating HBsAg
- To evaluate the proportion of HBeAg-positive CHB subjects who achieve HBeAg loss and seroconversion during 12 weeks of GS-9992 and after GS-9992 discontinuation through 48 weeks
- To evaluate the proportion of CHB subjects who achieve HBsAg loss during 12 weeks of GS-9992 and after GS-9992 discontinuation through 48 weeks
- To characterize steady-state pharmacokinetics of study drugs
- To evaluate the change from Baseline in quantitative HBsAg in CHB subjects during 12 weeks of GS-9992 and after GS-9992 discontinuation through 48 weeks

CCI [REDACTED]

[REDACTED]

[REDACTED]

[REDACTED]

[REDACTED]

#### 8.1.2. Primary Endpoint

##### Groups 1-3 and 5

The primary efficacy endpoint of this study is the proportion of subjects with  $\geq 0.5$  log10 IU/mL decline in HBsAg from Baseline at Week 12.

## Group 4

The primary efficacy endpoint of this study is the proportion of subjects with  $\geq 0.5 \log_{10}$  IU/mL decline in HBsAg from Baseline at Week 12 in virally suppressed CHB subjects.

